3.2 Exclusion Criteria

- 3.2.1 Patients who have had chemotherapy, radiotherapy, or immunotherapy within 4 weeks (6 weeks for nitrosoureas or mitomycin C) prior to entering the study or those who have not recovered from adverse events due to agents administered more than 4 weeks earlier.
- 3.2.2 Patients may not be receiving any other investigational agents, including extracorporeal photopheresis. Patients may not have received monoclonal antibody therapy within 6 weeks.
- 3.2.3 Patients with known brain metastases should be excluded from this clinical trial because of their poor prognosis and because they often develop progressive neurologic dysfunction that would confound the evaluation of neurologic and other adverse events.
- 3.2.4 History of allergic reactions attributed to compounds of similar chemical or biologic composition to imatinib mesylate.
- 3.2.5 Patients receiving any of the following medications or substances that are inhibitors or inducers of P450 3A4 are ineligible. Use of the following medications must be discontinued at least two weeks prior to starting therapy:
 - 1. Alfuzosin

2. Aprepitant
3. Carbamazepine
4. Clarithromycin
5. Eletriptan
6. Erythromycin
7. Pimozide
8. St John's Wort
9. Warfarin

A list of medications and substances known or with the potential to interact with the P450 3A4 isoenzyme is provided in Section 8. Imatinib mesylate is likely to increase the blood level of drugs that are substrates of CYP2C9, CYP2D6 and CYP3A4/5. Close monitoring is warranted when using agents metabolized by these enzymes. Grapefruit juice should not be consumed while on therapy.

- 3.2.6 Prior treatment with imatinib mesylate or other tyrosine kinase inhibitor after the date of transplant.
- 3.2.7 Uncontrolled intercurrent illness including, but not limited to, ongoing or active infection, symptomatic congestive heart failure, unstable angina pectoris, cardiac arrhythmia, pulmonary, hepatic, or other organ dysfunction, or psychiatric illness/social situations that would limit compliance with study requirements or compromise the patient's ability to tolerate protocol therapy.
- 3.2.8 Pregnant women are excluded from this study because imatinib mesylate is an agent with the potential for teratogenic or abortifacient effects. Because there is an unknown but potential risk for adverse events in nursing infants secondary to treatment of the mother with imatinib mesylate, breastfeeding should be discontinued if the mother is treated with imatinib mesylate.
- 3.2.9 HIV-positive patients on combination antiretroviral therapy are ineligible because of the potential for pharmacokinetic interactions with imatinib mesylate and the possibility of associated severe immunosuppression.
- 3.2.10 Patients with active hepatitis C or hepatitis B infection as defined by seropositivity for hepatitis C or hepatitis B (HepBSAg) and elevated transaminases, as GVHD manifestations involving the liver will be indistinguishable and drug-toxicity uninterpretable.
- 3.2.11 Persistent malignancy, requiring ongoing therapy.

3.3 Inclusion of Women and Minorities

Both men and women and members of all races and ethnic groups are eligible for this trial.

4 REGISTRATION PROCEDURES

Authorized staff must register an eligible candidate with NCI Central Registration Office (CRO) within 24 hours of signing consent. A registration Eligibility Checklist from the web site (<http://home.ccr.cancer.gov/intra/eligibility/welcome.htm>) must be completed and faxed to [contact]. After confirmation of eligibility at Central Registration Office, CRO staff will call pharmacy to advise them of the acceptance of the patient on the protocol prior to the release of any investigational agents. Verification of Registration will be forwarded electronically via e-mail to the research team. A recorder is available during non-working hours. Also, the CRO will be notified for removal of patients from study as defined in section 5.5.

5 TREATMENT PLAN

5.1 Imatinib Mesylate Administration

This is an open-label pilot study of oral imatinib mesylate for ScGVHD. Adult patients will receive 100 mg imatinib mesylate daily and pediatric patients will be dosed at 65 mg/m² daily (100 mg maximum) for 28 days. If tolerated, after 28 days, adult patients will be increased to 200 mg daily and pediatric patients will be increased to 130 mg/m² (200 mg maximum). If the 100mg (or 65mg/m²) dose is not tolerated due to unacceptable toxicity within the first 28 days despite following the dosing delay guidelines (section 6.0), the drug will be discontinued, except for patients taking 100mg daily who are also on potent CYP3A4 inhibitors. This group will be allowed dose reduction to 50mg. Children with a BSA < 0.97 (starting dose 50mg) who do not tolerate the drug during the first 28 days will be taken off study because dose reduction below 50mg is not possible with the 100mg tablets. Treatment cycles are continuous 28-day cycles with no rest period between cycles.

Imatinib mesylate is supplied as 100 mg tablets. Adult patients will initially receive 100 mg imatinib mesylate daily and pediatric patients will be dosed at 65 mg/m² daily (100 mg maximum, see nomogram below). After 1 month, adult patients will increase to 200 mg daily and pediatric patients will receive 130 mg/m² daily. Individual patient dosages will be rounded to the nearest 50 mg increment. Tablets are scored and the 100 mg tablets may be cut into achieve 50 mg dosing. According to the package insert, tablets may be dispersed in a glass of water or apple juice, stir until disintegrated and administer immediately. Since no long-term stability data are available, the administration of imatinib suspension should not be delayed. Patient should take drug with a meal and a large glass of water (patients who dissolve their tablets in liquid do not need to drink additional water). See Appendix Q for patient instructions.

The product labeling for imatinib mesylate provides dosing guidelines for patients with renal dysfunction, as defined by the following criteria (Prod Info GLEEVEC® oral tablets, 2010):

Renal Dysfunction Definitions (based on Product labeling)

Mild CrCL = 40-59 mL/min

Moderate CrCL = 20-39 mL/min

Severe CrCL = <20 mL/min

Mild renal dysfunction

The product labeling cautions that dose reduction may be needed at higher dosages of imatinib mesylate for patients with mild renal dysfunction. However, because patients on this protocol receive a low starting dose (100mg), dose adjustment will not be made for patients with mild renal dysfunction (creatinine clearance ≥ 40 ml/min).

Moderate renal dysfunction

As recommended by the product labeling guidelines (Prod Info GLEEVEC® oral tablets, 2010), patients with moderate renal dysfunction will decrease the starting dose by 50%. Therefore, adult patients and pediatric patients with BSA ≥ 0.97 will initially receive 50mg imatinib mesylate daily. After 1 month, adult patients and pediatric patients with BSA ≥ 0.97 and moderate renal dysfunction will increase to 100 mg daily if tolerated. Treatment and dose reductions will be based on estimated glomerular filtration rate (eGFR) and not on serum creatinine for patients with moderate renal dysfunction.

Children with a BSA < 0.97 (normal starting dose 50mg) with moderate renal dysfunction (creatinine clearance 30 -39ml/min) are ineligible because dose reduction is not possible below 50 mg.

Adult and pediatric patients with renal dysfunction between 20-30ml/min and with severe dysfunction (<20 ml/min) are not eligible for treatment.

Dose Nomogram for Pediatric Patients

65 mg/m ² /d		130 mg/m ² /d	
BSA [m²]	Dose [mg]	BSA [m²]	Dose [mg]
		0.38 – 0.57	50
0.58 – 0.96	50	0.58 – 0.96	100
≥ 0.97	100	0.97 – 1.34	150
		≥ 1.35	200

Patients receiving concomitant CYP3A4 inducers will have the starting dose of imatinib increased by 50%. The starting dosing of imatinib will be 150 mg/day for adult patients and 100 mg/m²/day for pediatric patients on concomitant CYP3A4 inducers. According to the package insert, tablets may be dispersed in a glass of water or apple juice, stir until disintegrated and administer immediately. Patients receiving concomitant CYP3A4 inhibitors (itraconazole, ketoconazole, posaconazole, voriconazole and fluconazole) will be monitored closely for toxicity, but routine dose reduction will not be employed.

Treatment will be administered on an outpatient basis. Reported adverse events and potential risks are described in Section 7. Appropriate dose modifications for imatinib mesylate are described in Section 6. No investigational or commercial agents or therapies other than those described below may be administered with the intent to treat the patient's cGVHD.

Patient Instructions (See **Appendix Q: Patient Instructions**)

It is best to take this medicine with food and a large glass of water. If the patient is not able to swallow the tablet, he/she may dissolve the tablet in a glass of water or apple juice. If taking ½ tablet (50 mg), it should be dissolved in 1 ounce (1/8 cup) of water or juice. If taking 100 mg (1 tablet), it should be dissolved in 2 ounces (1/4 cup) of water or juice. If taking 200 mg (2 tablets), it should be dissolved in 4 ounces of water or juice. If you are taking 300 mg (3 tablets), dissolve it in 6 ounces (about 3/4 cup) of water or juice. Stir with a spoon and drink immediately after the tablet has dissolved.

Patients that require a ½ tablet (50 mg) dose will be required to split the scored tablets. Parents will be taught the proper technique for breaking tablets according to standard procedure. Do not handle broken tablets with unprotected hands. Patients should wear gloves when handling broken or cut tablets.

Store the medicine in a closed container at room temperature, away from heat, moisture, and direct light.

If a dose is missed, it should be taken as soon as possible. If it is almost time for the next dose, wait until then to use the medicine and skip the missed dose. Do not use extra medicine to make up for a missed dose.

Grapefruit juice should be avoided.

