3 PATIENT SELECTION

3.1 Eligibility Criteria

- 3.1.1 ScGVHD manifesting after at least 100 days following allogeneic hematopoietic stem cell transplantation is considered diagnostic for cGVHD according to NIH cGVHD Consensus Statement diagnostic criteria [10,13]. The diagnosis can be made clinically or by histopathology. The diagnosis must be confirmed by the principal investigator (PI), or lead associate investigator (LAI). Skin biopsies will be reviewed by the NCI Laboratory of Pathology to confirm the diagnosis of ScGVHD.
- 3.1.2 Patients must have measurable limitation in range of motion, defined as ScGVHD with or without fasciitis, restricting range of motion (ROM) of at least one joint with a minimum deficit of 25%. See Section 11 for the evaluation of measurable disease.
- 3.1.3 Prior therapy: Patients must have cGVHD refractory to at least one treatment regimen for cGVHD. One prior regimen must have included systemic corticosteroids at the equivalent prednisone dosing of 1mg/kg/day x 14 days. Patients in whom calcineurin inhibitors or

corticosteroids are medically contraindicated may also be eligible for enrollment. Patients who have had stabilization of disease on calcineurin inhibitors or steroids, but in whom these medications cannot be tapered without disease flare are also eligible. Patient must be on stable or tapering immunosuppressive regimen for at least one month.

- 3.1.4 Age: 4 years of age or older at the time of enrollment. Lower age limit set by lower established age limit norms of ROM scores for measurement criteria.
- 3.1.5 Life expectancy of greater than 6 months.
- 3.1.6 Karnofsky $\geq 60\%$; see Appendix A.
- 3.1.7 Patients must be platelet transfusion and growth factor independent at the time of study entry. Patients must have adequate organ and marrow function as defined below. Patients with Gilbert syndrome are excluded from the requirement of a normal bilirubin. (Gilbert syndrome is found in 3-10% of the general population, and is characterized by mild, chronic unconjugated hyperbilirubinemia in the absence of liver disease or overt hemolysis).

- X absolute neutrophil count $\geq 1,000/\text{mcL}$
- X platelets $\geq 50,000/\text{mcL}$
- X total bilirubin $< 3x$ upper limit of normal
- X AST(SGOT)/ALT(SGPT) $< 5 x$ upper limit of normal
- X creatinine age-adjusted within normal limits

OR

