creatinine clearance $\geq 30 \text{ mL/min/1.73 m}^2$ for adults and pediatric patients with BSA $\geq 0.97 \text{ m}^2$ with creatinine levels above institutional normals and $\geq 40 \text{ mL/min/1.73 m}^2$ for pediatric patients with BSA $< 0.97 \text{ m}^2$

Age (Years)	Maximum Serum Creatinine (mg/dL)
< 5	0.8
5 < age < 10	1.0
10 < age < 15	1.2
>15	1.5

- 3.1.8 Normal cardiac function for age as determined by ECHO or MUGA (normal LV function as measured by ejection fraction or shortening fraction).
- 3.1.9 The effects of imatinib mesylate on the developing human fetus at the recommended therapeutic dose are unknown. For this reason, women of child-bearing potential and men must agree to use adequate contraception (hormonal or barrier method of birth control; abstinence) prior to study entry, for the duration of study participation, and for six months following completion of therapy. Should a woman become pregnant or suspect she is pregnant while participating in this study, she should inform her treating physician immediately.
- 3.1.10 Ability to understand and the willingness to sign a written informed consent document. All patients or their legal guardian (for patients <18 years old) must sign an IRB approved document of informed consent (cGVHD natural history or any NCI protocol allowing for screening procedures) prior to performing studies to determine patient eligibility. After confirmation of patient eligibility all patients or their legal guardian must sign the protocol-specific informed consent. Pediatric patients will be included in age appropriate discussions and age appropriate assent will be obtained in accordance with NIH guidelines.
- 3.1.11 Durable Power of Attorney (DPA): All patients 18 years of age at the time of enrollment will be offered the opportunity to assign DPA so that another person can make decisions about their medical care if they become incapacitated or cognitively impaired.

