11.1 On Study Protocol Evaluation

11.1.1 Pre-treatment Evaluation: Pre-treatment tests should be performed within 8 weeks prior to enrollment on the trial unless otherwise stated. The evaluation required prior to starting treatment is listed in table form in Appendix B. The evaluation may be performed as part of enrollment onto NIH Protocol #04-C-0281 entitled: "Prospective Assessment of Clinical and Biological Factors Determining Outcomes in Patients with Chronic Graft-Versus-Host Disease". Attempts will be made to enroll patients on this study.

- 1. History and Physical Examination:** All patients should have a complete history (including prior and concurrent therapy) and physical examination including documentation and scoring of cGVHD, performance status, and signs and symptoms. Height, weight and body surface area must be recorded. All physical exam and cGVHD findings should be recorded and documented as per Appendices D-H. This evaluation should be within 2 weeks of starting therapy.
- 2. Hematology:** PT/PTT, fibrinogen, complete blood counts, with differential and platelet count. To be performed within 72 hours prior to starting therapy. If there is significant change in clinical status, all eligibility labs will be repeated prior to starting therapy.
- 3. Chemistries:** Electrolytes (including sodium, potassium, chloride, CO₂, calcium, phosphorus and magnesium), creatinine, BUN, glucose, SGOT, alkaline phosphatase, SGPT, and bilirubin. Serum iron studies (Fe, ferritin, and transferrin). To be performed within 72 hours prior to starting therapy. If there is significant change in clinical status, all eligibility labs will be repeated prior to starting therapy. For patients with serum creatinine levels above the age-adjusted normal limits, a 24 hour urine collection for creatinine clearance and eGFR will be performed.

4. Other lab tests: Infectious disease screening for CMV, HSV, EBV, HIV, HTLV, HBV, HCV, VZV, Lymphocyte Phenotyping TBNK and immunoglobulin levels. Research labs as defined in section 9.1.
5. Urine or Serum Pregnancy test: For all females of childbearing potential. This test is to be performed within 7 days prior to enrollment on the trial.
6. Pulmonary Function Tests (PFTs): All patients. Patients requiring a pediatric PFT lab will be evaluated by Children's National Medical Center (CNMC) Department of Pulmonology. Calculate lung function score (LFS) based on findings (Appendix O),
7. Radiographic Evaluation:

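### Renal eligibility is set in mL/min/1.73 m² but the renal dose bands and exclusions are in plain mL/min, so some patients with raised creatinine get conflicting answers from Sections 3.1.7 and 5.1

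*Combined protocol and SAP*

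**What the plan says.** - **Section 3.1.7 (eligibility).** There are two alternative routes. One is "creatinine age-adjusted within normal limits", with no clearance value needed. The other is a clearance threshold for patients "with creatinine levels above institutional normals". That threshold is indexed to body surface: "creatinine clearance $\geq 30 \text{ mL/min/1.73 m}^2$ for adults and pediatric patients with BSA" of 0.97 m² or more, and 40 on the same scale for children with BSA below 0.97 m².
- **Section 5.1 (dosing).** The bands are attributed to the product labeling and carry no index: "Mild CrCL = 40-59 mL/min", "Moderate CrCL = 20-39 mL/min", and severe below 20 mL/min. Mild dysfunction brings no dose change; moderate dysfunction halves the starting dose. Children with BSA below 0.97 m² and 30-39 mL/min are ineligible. For everyone: "Adult and pediatric patients with renal dysfunction between 20-30ml/min and with severe dysfunction (<20 ml/min) are not eligible for treatment".
- **Which measure.** The bands in 5.1 are labelled as creatinine clearance, but treatment and dose reductions in moderate dysfunction rest on eGFR, with no unit. Section 6.1 repeats the eGFR basis. Section 11.1.1 says that, when creatinine is above the age-adjusted limit, "a 24 hour urine collection for creatinine clearance and eGFR will be performed". It gives no unit for either and does not say which one governs.

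**The concern.** Eligibility and dosing should be read off one renal value on one scale. Here one section indexes to 1.73 m² and the other does not. The two scales coincide only at a BSA of 1.73 m², and the protocol enrols from age 4 with a nomogram reaching well below that.

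Three decisions depend on the scale:

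- whether a patient may be treated at all;
- the starting dose, and the dose after one month, under 5.1;
- which rows of the dose-modification table in 6.1 apply, because its footnote reserves the separate eGFR handling for moderate renal dysfunction.

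The tolerability analysis is also touched. Section 14.1.1 asks for 8 or more of the first 10 patients to tolerate 200 mg, while 5.1 takes patients with moderate dysfunction only to 100 mg. How such a patient counts is not stated, so the renal class could matter to a result decided on 10 patients.

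**Working it through.** The plan states no figure to reproduce. The check is a unit conversion:

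absolute clearance (mL/min) = indexed clearance (mL/min/1.73 m²) × BSA / 1.73

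**Inputs.** Eligibility thresholds of 30 and 40 mL/min/1.73 m² and the BSA split at 0.97 m² (3.1.7); bands and exclusions at 20, 30 and 40 mL/min (5.1); BSA 0.58-0.96 m² for the smaller children (starting-dose nomogram in 5.1). I treat the bands as contiguous, so that moderate ends where mild begins, at 40.

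**Step 1: ignore the units.** For BSA below 0.97, 3.1.7 admits from 40 and 5.1 excludes everything below 40. For all others, 3.1.7 admits from 30 and 5.1 excludes 20-30 and below. The rules agree except at exactly 30, which 3.1.7 admits and 5.1 places in an excluded range. The remaining conflict therefore comes from the units alone.

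**Step 2: BSA below 0.97, units as printed.** The first result is 40 × BSA / 1.73. The second is the indexed value needed to clear the 5.1 exclusions, 40 × 1.73 / BSA.

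| BSA (m²) | 40 indexed, in mL/min | Indexed value equal to 40 mL/min |
|---|---|---|
| 0.58 | 13.4 | 119.3 |
| 0.70 | 16.2 | 98.9 |
| 0.80 | 18.5 | 86.5 |
| 0.90 | 20.8 | 76.9 |
| 0.96 | 22.2 | 72.1 |

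A child entering by the clearance route with an indexed value from 40 up to the last column passes 3.1.7 and is ineligible under 5.1.

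**Step 3: BSA 0.97 and above.** The formulas are 30 × BSA / 1.73, 30 × 1.73 / BSA and 40 × 1.73 / BSA.

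| BSA (m²) | 30 indexed, in mL/min | Indexed value equal to 30 mL/min | Indexed value equal to 40 mL/min |
|---|---|---|---|
| 0.97 | 16.8 | 53.5 | 71.3 |
| 1.10 | 19.1 | 47.2 | 62.9 |
| 1.35 | 23.4 | 38.4 | 51.3 |
| 1.50 | 26.0 | 34.6 | 46.1 |
| 1.73 | 30.0 | 30.0 | 40.0 |

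Below BSA 20 × 1.73 / 30 = 1.15 m², a patient at the 3.1.7 threshold is in the severe band of 5.1. Between that and 1.73 m², the same patient is in the excluded 20-30 range.

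**Step 4: starting dose.** At BSA 1.00, 60 mL/min/1.73 m² is 60 × 1.00 / 1.73 = 34.7 mL/min. Read as indexed, it is above 40 and the starting dose is 100 mg. Read as printed, it is moderate and the starting dose is 50 mg. At BSA 1.50, 44 indexed is 44 × 1.50 / 1.73 = 38.2 mL/min: mild on one scale, moderate on the other.

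**Step 5: BSA above 1.73 m².** The direction reverses. At BSA 2.00, 32 mL/min is 32 × 1.73 / 2.00 = 27.7 mL/min/1.73 m². With raised creatinine, that patient fails 3.1.7 but is not excluded by 5.1. Likewise 36 indexed is 36 × 2.00 / 1.73 = 41.6 mL/min: moderate if read as indexed, mild as printed.

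**The case against.** The best defence is that the two sections are one rule written twice. They share the 30 and 40 cut-offs and the BSA split, so the natural explanation is that 5.1 dropped the index when it repeated 3.1.7. That is plausible, and it would make this a clerical slip. It does not settle the matter: 5.1 attributes its bands to labeling in mL/min, nothing says that its values are indexed, and staff following the text as printed would get different answers.

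The defence does rule out several stronger inferences that a reader might draw:

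- *That small children who pass 3.1.7 are in general excluded by 5.1.* They are not. A child with age-adjusted normal creatinine enters without a clearance value, and 11.1.1 requires one only when creatinine is raised. The conflict is confined to the clearance route and to the ranges above.
- *That both scales will be on file.* Section 11.1.1 names two measures, not two scales. Either could be reported indexed or absolute.
- *That the scales differ by about twofold in children.* The ratio is 1.73 / BSA: 3.0 at 0.58, 1.8 at 0.97 and 1.3 at 1.35.
- *That Section 6.1 has cut-offs to convert.* It has none in mL/min; it works from CTCAE grades and refers to eGFR and moderate dysfunction.
- *That the tolerability result is shown to be affected.* The number of patients concerned cannot be derived from the documents, and the cohort is at most 13.

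**Conclusion.** The point holds as an internal inconsistency. As printed, 3.1.7 and 5.1 can give opposite eligibility answers, or different starting-dose bands, for one patient with raised creatinine whose BSA is well below 1.73 m². At or near 1.73 m² the mismatch is small, and above it the direction reverses. No stated figure is miscalculated.

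This rests on reading the units literally and on the patient entering by the clearance route. If 5.1 was meant to be indexed, the conflict disappears apart from the value of exactly 30, but the documents do not establish that. Nor do they establish that any patient was wrongly treated, or which scale is correct. The sections should be reconciled because the classification governs eligibility and dose; the number of patients affected is unknown and may be small.

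**What to change.** Reconcile 3.1.7 and 5.1 to one stated unit and one stated measure, either 24-hour creatinine clearance or eGFR. Name that measure and unit again wherever 5.1 and 6.1 refer to eGFR or moderate renal dysfunction, and in 11.1.1 say which of the two collected values governs. In the same edit, resolve the overlap at exactly 30. If the scales are deliberately different, say so and give the conversion and the order of precedence.

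The choice of scale, cut-offs and doses is for the sponsor. The cost is a wording amendment to a few paragraphs, with no new test, visit or patient.

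### The pediatric starting dose on CYP3A4 inducers has no maximum, and the sections disagree on whether the 50% increase carries into the second dose step

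*Combined protocol and SAP*

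**What the plan says.** All references are to the combined protocol and SAP.

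- **Ordinary start (Section 5.1).** Adults receive 100 mg daily, and "pediatric patients will be dosed at 65 mg/m² daily (100 mg maximum) for 28 days". The 65 mg/m² nomogram column gives 50 mg at BSA 0.58–0.96 and 100 mg from 0.97.
- **Ordinary step 2 (Section 5.1).** After 28 days, if the first dose is tolerated, adults go to 200 mg and children to 130 mg/m², with a 200 mg maximum.
- **Rounding (Section 5.1).** "Individual patient dosages will be rounded to the nearest 50 mg increment".
- **Inducer start (Section 5.1).** "Patients receiving concomitant CYP3A4 inducers will have the starting dose of imatinib increased by 50" percent, followed by: "The starting dosing of imatinib will be 150 mg/day for adult patients and 100 mg/m²/day for pediatric patients on concomitant CYP3A4 inducers". No maximum follows the pediatric figure, and the nomogram has no inducer column.
- **Section 6.2.** Inducer patients start 50% higher, with a reference back to Sections 5.1 and 5.2.4.
- **Section 5.2.4.** Use of imatinib with a potent inducer (phenobarbital, phenytoin, rifampin) raises the imatinib dose by 50%. This is not limited to the starting dose.
- **Patient instructions in Section 5.1.** These include the line "If you are taking 300 mg (3 tablets), dissolve it in 6 ounces".

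**The concern.** Both ordinary pediatric doses are capped at the adult dose for the same step, so a large child never receives more than an adult. The inducer start breaks that pattern. Taken literally, it gives the largest pediatric patients more than an adult on the same inducer, and more than the 50% increase that the rule announces. It also removes the low first cycle for them: 200 mg is already the ordinary step-2 maximum.

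The second issue is scope. A prescriber with an adult on rifampin who reaches day 29 finds 200 mg in Section 5.1 and, through Section 5.2.4, 300 mg. Amendment E (Section 14.1.1) exists to test tolerability at 200 mg after a 100 mg start, so the protocol should say which dose is meant.

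**Working it through.** **1. Reproduce the stated inducer doses.**

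- Adult: 100 mg × 1.5 = 150 mg, as stated.
- Pediatric: 65 mg/m² × 1.5 = 97.5 mg/m², stated as 100 mg/m² (100/65 = 1.538, or +53.8%). The stated figure is the 50% increase, rounded.

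**2. Check the rounding rule against the protocol's own table.** Multiplying 130 mg/m² by BSA and rounding to the nearest 50 mg should give the step-2 nomogram:

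- 0.57 → 74.1 → 50 mg; 0.58 → 75.4 → 100 mg
- 0.96 → 124.8 → 100 mg; 0.97 → 126.1 → 150 mg
- 1.34 → 174.2 → 150 mg; 1.35 → 175.5 → 200 mg

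All breaks match.

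**3. Apply the rule to the inducer start.** Dose = 100 mg/m² × BSA, nearest 50 mg, ties rounded up (an assumption), compared with the 65 mg/m² nomogram dose.

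| BSA (m²) | Inducer start (mg) | Ordinary start (mg) | Change |
|---|---|---|---|
| 0.58–0.74 | 50 | 50 | +0% |
| 0.75–0.96 | 100 | 50 | +100% |
| 0.97–1.24 | 100 | 100 | +0% |
| 1.25–1.74 | 150 | 100 | +50% |
| 1.75–2.24 | 200 | 100 | +100% |

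From BSA 2.25 the written rule gives 250 mg. Rounding ties down moves only the single break points. Using 97.5 mg/m² moves the last break from 1.75 to 1.80 (97.5 × 1.80 = 175.5).

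**4. Separate the missing maximum from the rounding.** Before rounding, the ordinary 100 mg cap binds from BSA 100/65 = 1.54. At BSA 1.75 the unrounded inducer dose is 175 mg against a capped 100 mg, which is +75%; rounding to 200 mg makes it +100%. So in the top band most of the excess is there before rounding. With a maximum of 1.5 × 100 = 150 mg, every BSA from 1.25 upward gets 150 mg, which is +50% and equals the adult inducer start.

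Below BSA 1.25 a maximum changes nothing. There the mismatch comes from 50 mg steps: at BSA 0.58–0.96 an exact increase would be 75 mg, which cannot be dispensed. At 0.97–1.24 the ordinary dose has already been rounded up, and 100 mg is 103 to 81 mg/m² (100/0.97 to 100/1.24).

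**5. Step 2 under the two readings.**

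| | Start only (5.1, 6.2) | Any concurrent use (5.2.4) |
|---|---|---|
| Adult | 200 mg | 200 × 1.5 = 300 mg |
| BSA 0.58–0.96 | 100 mg | 150 mg |
| BSA 0.97–1.34 | 150 mg | 225 mg (not dispensable) |
| BSA ≥ 1.35 | 200 mg | 300 mg |

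On the start-only reading, a child of BSA 1.75–2.24 goes from 200 mg to 200 mg, so there is no step-up. With the 150 mg maximum the step is 150 to 200 mg, as for an adult.

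**The case against.** The strongest reply is that 100 mg/m² is a fair rounding of 97.5, and that the protocol openly accepts coarse tablets. The ordinary nomogram misses its own ratio in the same way: doubling 65 to 130 mg/m² yields only 100 to 150 mg at BSA 0.97–1.34. This stands. A reader of the first table might infer that the pediatric dose is an arithmetic error, or that it fails in every band but one. The documents do not support that; below BSA 1.25 the pattern is a product of rounding.

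A reader might also infer that two prescribers following Section 5.1 would give the same child different doses throughout. Below BSA 1.75 the explicit mg/m² dose and the rounding rule give one answer, apart from exact ties. Only from 1.75 is there real doubt, because a careful prescriber might infer a 150 mg limit that is nowhere stated.

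On step 2, it can be argued that Section 5.2.4 complements Section 5.1, since Section 6.2 cites both as agreeing and neither 5.1 nor 6.2 forbids a later increase. That makes it a question of scope, but the reader still meets two doses. The 300 mg instruction line does not settle it. It may be left over from the 400 mg design, and its list omits 150 mg, a current nomogram dose.

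It is tempting to ask for changes to the reduction and stopping rules as well: Section 6.1, the 28-day rule ("dose is not tolerated due to unacceptable toxicity within the first 28 days despite following the dosing delay guidelines") and the small-child rule ("Children with a BSA < 0.97 (starting dose 50mg) who do not tolerate the drug during the first 28 days"). The documents do not require this. Cutting 200 mg to 100 mg for toxicity is a legitimate choice even for a patient who started at 150 mg. The small-child rule states its action clearly, although its stated reason fits an inducer patient poorly. Section 6 also sends every dose modification to the principal or lead associate investigator.

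Finally, inducers lower imatinib exposure, 200 mg is an ordinary step-2 dose, and these patients are monitored closely for toxicity. An inference that patients would be harmed is not supported.

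**Conclusion.** The point holds in two parts. First, as written, the pediatric inducer start gives 200 mg at BSA 1.75–2.24, against the 150 mg that the 50% rule and the adult dose imply. Second, Sections 5.1 and 6.2 differ from Section 5.2.4 in scope, so an adult's step-2 dose on an inducer is 200 or 300 mg depending on the section read.

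Severity is minor. Reach is limited to users of the three inducers named in Section 5.2.4, in a second cohort of at most 13. The number of such users is not given, and the missing maximum matters only for large pediatric patients among them. A reader might infer that the 8-of-10 tolerability rule or the power statement is undermined; neither calculation changes, and nothing in the documents shows that the outcome would.

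The conclusion assumes nearest-50 mg rounding with ties up, the 65 mg/m² nomogram as comparator, and that Section 5.1 means the potent inducers listed in Section 5.2.4. Appendix Q was not in the text available, so the missing statements are missing from the text that was.

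**What to change.** 1. In Section 5.1, add a 150 mg maximum after the pediatric inducer start of 100 mg/m²/day.
2. In Section 5.2.4, say whether the 50% increase applies to the starting dose only or also to step 2, and give the resulting step-2 dose, so that it agrees with Sections 5.1 and 6.2. If start only, step 2 stays at 200 mg for adults and follows the 130 mg/m² nomogram for children. If both steps, it is 300 mg for adults and BSA 1.35 or more, 150 mg at BSA 0.58–0.96, and one named dose at 0.97–1.34, because 225 mg cannot be dispensed. If both steps are chosen, amend Sections 5.1 and 6.2 to match. The choice is clinical. The moderate renal dysfunction text in Section 5.1 is a model: it states both the start and the step-2 dose in mg.

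An inducer column in the nomogram would be convenient but is not required. Sections 6.1 and the 28-day rule can stay as they are.

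The cost is one maximum and a sentence or two of text. No patients, visits or procedures are added.
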